6.2.3 Post-Entry Evaluations (for participants who meet Step 2 entry criteria)

Days 1-7 (Treatment)

Participants must begin treatment within 24 hours after registration/randomization. Participants will receive their assigned dose of INH in the morning on an empty stomach, defined as nothing by mouth except water and study medications 2 hours pre-dose and 1 hour post-dose.

Day 8 (Discharge)

Those participants enrolled in a treatment group will be discharged from the hospital on Day 8. Upon discharge from the hospital and no later than Day 10, participants will be referred to the standard local TB treatment.

Final Visit

This visit will occur 14 (± 3) days after the final dose of study medications to evaluate for evidence of delayed toxicity and to follow up on any adverse events (AEs) that occurred during the study.

6.2.4 Discontinuation Evaluations

Evaluations for Randomized or Registered Participants Enrolled to Step 2 Who Do Not Start Study Treatment

All case report forms (CRFs) must be completed and keyed for the period up to and including Step 2 Day 0.

Evaluations for Registered Participants Not Enrolled to Step 2

All CRFs must be completed and keyed for the period up to and including Step 1 Day 0. An off-study form will be completed for these participants at Step 1 Day 0. No premature discontinuation evaluations are needed.

Premature Study Discontinuation Evaluations

If study withdrawal occurs, the participant will be asked to complete a premature discontinuation visit. Assessments to be performed at the premature discontinuation visit are listed in [section 6.1](#). Participants who prematurely discontinue treatment will be prematurely discontinued from the study.

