7.0 CLINICAL MANAGEMENT ISSUES

7.1 Toxicity

Only toxicities related to study medications will be considered in the toxicity management section. The grading system for drug toxicities is located in the DAIDS AE Grading Table, Version 1.0, December 2004 (Clarification, August 2009), located at the DAIDS RSC web site: <http://rsc.tech-res.com/clinical-research-sites/safety-reporting/daids-grading-tables>.

7.1.1 Grade 1

Study participants who develop a Grade 1 AE or toxicity may continue study medications at the discretion of the site investigator.

If participants choose to discontinue study drug, the A5312 Clinical Management Committee ([contact]) should be notified within 48 hours. The site should complete the premature discontinuation evaluations, as per [section 6.1.2](#), within 7 days after stopping study medications.

7.1.2 Grade 2

Participants who develop a Grade 2 AE or toxicity may continue study drugs, at the discretion of the site investigator, and will be followed carefully.

If participants choose to discontinue study drug, the A5312 Clinical Management Committee should be notified within 48 hours. The site should complete the premature discontinuation evaluations, as per [section 6.1.2](#), within 7 days after stopping study medications.

Grade 2 clinical or laboratory abnormalities that are deemed likely related to study drug will be followed to stabilization or resolution to Grade ≤ 1 . Evaluations and the frequency of follow-up visits are at the discretion of the site investigator. The A5312 Clinical Management Committee should be notified of any requirements for continuing follow-up of toxicities beyond 7 days after stopping study medications.

7.1.3 Grade 3

Unless the site investigator has compelling evidence that the Grade 3 AE or toxicity is not related to the study drug, the participant must permanently discontinue the study drug. The A5312 Clinical Management Committee should be notified within 48 hours. The site should complete the premature discontinuation evaluations, as per [section 6.1.2](#), within 7 days after stopping study medications.

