Clinical or laboratory abnormalities of Grade 3 that are deemed likely related to study medication will be followed to stabilization, resolution to Grade ≤ 1 , or return to baseline. Evaluations and the frequency of follow-up visits are at the discretion of the site investigator. The A5312 Clinical Management Committee should be notified of any requirements for continuing follow-up of toxicities beyond 7 days after stopping study medications.

7.1.4 Grade 4

Any participant with Grade 4 toxicity will be immediately and permanently discontinued from the study. The site should complete the premature discontinuation evaluations, as per [section 6.1.2](#), within 7 days after stopping study medications.

Clinical or laboratory abnormalities of Grade 4 that are deemed likely related to study medication will be followed to stabilization, resolution to Grade ≤ 1 , or return to baseline. Evaluations and the frequency of follow-up visits are at the discretion of the site investigator. The A5312 Clinical Management Committee should be notified of any requirements for continuing follow-up of toxicities beyond 7 days after stopping study medications.

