8.0 CRITERIA FOR DISCONTINUATION

8.1 Premature Study Discontinuation

- Inability to produce an overnight sputum sample of sufficient quality and quantity over a 16-hour collection period on Step 2 Day 0
- Grade ≥ 3 drug-related AE or toxicity or any Grade 4 AE or toxicity (see [section 7.1](#) Toxicity)
- Requirement for prohibited concomitant medications (see [section 5.4](#))
- Failure by the participant to comply with inpatient hospital stay
- Pregnancy

- Nonadherence with one or more doses of study treatment
- Development of another medical condition that makes the administration of one or more planned doses of study drug inadvisable
- Inability to provide a study-required sputum sample at any time through day 8
- Request by the participant to stop study treatment or withdraw
- It is the investigator's judgment that it is no longer in the best interest of the participant to continue study participation.
- At the discretion of the ACTG, IRB/EC, NIAID, Office for Human Research Protections (OHRP), or other government agencies as part of their duties, or the investigator.

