## 3 Definitions

### 3.1 Analysis Population

Safety population: Safety analyses will be intent-to-treat and include all eligible participants who took at least one dose of study drugs.

Efficacy population: The primary analyses will use a per-protocol approach, limited to participants who provide CFU and TTD data at both study entry and Day 7. For the model based analysis, all randomized participants who had at least one CFU count or TTD will be included.

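### Participants who take INH but stop early have no scheduled 14 ± 3 day delayed-toxicity visit, so new Grade 2 or higher events are counted over unequal windows

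*Protocol*

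**What the plan says.** Protocol 6.2.3 gives the Final Visit its timing and purpose: "This visit will occur 14 (± 3) days after the final dose of study medications to evaluate for evidence of delayed toxicity". SAP 4.2 places the same visit at Day 21 ± 3.

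Protocol 6.2.4 ties the end of treatment to the end of study participation: "Participants who prematurely discontinue treatment will be prematurely discontinued from the study". The visit it provides is this: "If study withdrawal occurs, the participant will be asked to complete a premature discontinuation visit". It gives no timing. Section 7.1 does give a time, for stops under Grades 1 to 4: "within 7 days after stopping study medications". Section 6.3.6 puts the neuropathy examination at the Final Visit or, for early discontinuers, at the discontinuation visit.

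The list in 8.1 includes reasons that have nothing to do with toxicity, such as missing one dose or this one: "Inability to provide a study-required sputum sample at any time through day 8".

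Section 7.1 also requires some events to be followed further. For Grade 3: "Clinical or laboratory abnormalities of Grade 3 that are deemed likely related to study medication will be followed to stabilization". Grades 2 and 4 have similar provisions, none with a fixed end date, and the text foresees follow-up more than 7 days after stopping.

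Protocol 9.2.1.4 makes drug-related events of Grade 2 or higher a primary endpoint for all groups. SAP 3.1 says that safety analyses "include all eligible participants who took at least one dose of study drugs". SAP 4.3.1 tabulates new Grade 2 or higher signs, symptoms and laboratory events, with no provision for differing follow-up.

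**The concern.** The protocol considers delayed toxicity important enough for a dedicated visit, yet it schedules that visit only for people who stay on study. Anyone who took INH and left early remains in the denominator of the safety table with a shorter scheduled window for new events. A first Grade 2 transaminase rise 12 days after the last dose falls within a completer's scheduled follow-up. In an early stopper no scheduled visit would look for it.

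Part of the problem is that 8.1 treats failure of the EBA measurement as a reason to end safety observation. A missing sputum sample makes someone uninformative for EBA. It does not make their drug exposure uninformative for safety. The overnight collections start at about 4 pm and dosing is in the morning, so a failure of the Day 7 collection could remove a person who has already taken all seven doses.

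Replacement under 9.4 restores the number evaluable for EBA. It does not restore the missing safety window of the person replaced.

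**Working it through.** This is visit-day arithmetic. No power or variance calculation applies.

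**The plan's own figures.** Dosing runs Days 1 to 7 (Protocol 6.3.6). The Final Visit for a completer is 7 + 14 = Day 21, range 7 + 11 = Day 18 to 7 + 17 = Day 24, which agrees with SAP 4.2. The stated duration of about 23 days also reproduces: Day −2 to Day 21 is 21 + 2 = 23 days elapsed. Counting calendar days from Day −1 to Day 21 inclusive also gives 23. The stated duration thus rests on the Day 21 visit.

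**Early stoppers.** Let the last dose be on Day k, k = 1 to 6, and take the stopping date as the last-dose date (an assumption). Under 7.1 the discontinuation visit falls between Day k and Day k + 7.

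| | Completer | Early stop under 7.1 | Early stop for another reason |
|---|---|---|---|
| Last scheduled visit, days after last dose | 14 (11 to 17) | 0 to 7 | no timing stated |
| Last scheduled visit, study day | 21 (18 to 24) | at latest Day 8 (k = 1) to Day 13 (k = 6) | no timing stated |
| Days from first dose to that visit | 20 (17 to 23) | at most 7 (k = 1) to 12 (k = 6) | no timing stated |

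Difference in scheduled follow-up after the last dose:

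- smallest: 11 − 7 = 4 days
- target Final Visit against the latest discontinuation visit: 14 − 7 = 7 days
- largest: 17 − 0 = 17 days

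**Weight of one person.** The Group 3 target is 10 completing per dose cohort (Protocol synopsis, Sample Size). A replaced stopper who took a dose stays in the safety population, so one stopper is 1/(10 + 1) = 9.1% of that cohort. In a Group 1 cohort of 16 it is 1/(16 + 1) = 5.9%.

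**What 7.1 covers.**

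- A known, likely related Grade 2, 3 or 4 abnormality is followed until it settles, possibly beyond 14 days. There is no gap for that event.
- A new event that first appears after the discontinuation visit has no scheduled visit to detect it. The same holds for a Grade 1 abnormality that later becomes Grade 2.
- An event not judged likely related has no required follow-up after the discontinuation visit. Section 7.1.3 uses two standards here. The drug is stopped "Unless the site investigator has compelling evidence that the Grade 3 AE or toxicity is not related to the study drug", while continued follow-up is required only for abnormalities deemed likely related. An event between those standards stops the drug and then has no mandated follow-up.

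**Effect of applying 6.2.3 to everyone dosed.** The visit would fall on Day k + 14: Day 15 (12 to 18) for k = 1 and Day 20 (17 to 23) for k = 6. Scheduled follow-up would then be 11 to 17 days after the last dose for all.

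**The case against.** A reader might infer that the participants who had toxicity get the shortest safety follow-up of all. The documents do not support that. Sections 7.1.2 to 7.1.4 keep known, likely related Grade 2 to 4 abnormalities under observation with no end date, and such a person may be followed longer than a completer. The event that caused the stop has also already been recorded, so following it to resolution would not change an incidence count. Both points stand, and they limit the concern to additional or later events.

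It can be argued that 6.2.3 times the Final Visit from the last dose, not from completing seven days, and so covers everyone dosed. No sentence expressly exempts early stoppers. That reading is possible, but 6.2.4 takes them off study and 6.3.6 moves the neuropathy examination to the discontinuation visit, so the other reading is the more natural one. If sites could read it either way, the text needs settling.

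No document gives a rate of late events after a short INH course. Protocol 2.1 describes neurotoxicity as depending on dose and duration, and early stoppers have the least exposure. It also reports no treatment-related events of Grade 3 or above and no neuropathy in the *inhA* arms. Expedited reporting runs for a period set by a manual that is not in the documents, so some serious events may be captured anyway. A claim that late events are under-counted most at the doses that cause stopping would therefore be conjecture. None of this supplies a scheduled visit for non-serious Grade 2 events.

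**Conclusion.** The point holds as a gap in scheduled ascertainment. Dosed participants who leave early have no scheduled delayed-toxicity visit, and their scheduled follow-up after the last dose is 4 to 17 days shorter than a completer's when the stop falls under 7.1. For other stops the length is undefined. The primary safety endpoint is counted over these unequal windows without adjustment.

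This rests on reading 6.2.4 and 6.3.6 together and on taking the stopping date as the last-dose date. The number of early stoppers and their late-event rate are not in the documents, so the size of any undercount is unknown and a dose-related bias is not shown. It is worth correcting because the cost is low and safety is a primary objective.

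**What to change.** Reconcile Protocol 6.2.3, 6.2.4 and 8.1 so that stopping study drug, or failing EBA sampling, is separate from leaving safety follow-up. Every participant who took at least one dose of INH would keep the Final Visit already defined in 6.2.3, in addition to the discontinuation visit, unless consent is withdrawn. State a time for the discontinuation visit when the stop is not under 7.1.

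The two relatedness standards in 7.1.3 must be reconciled by the sponsor. That is a clinical-management matter and no rule is proposed here.

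If accrual has ended, the separate report on Version 3.0 participants foreseen in SAP section 5 can still give each participant's safety follow-up time after the last dose by cohort, identify those without the 14 ± 3 day visit, and state that late events could not be ascertained on the same footing in them.

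The cost is protocol wording and one existing visit for a few people, or one table. The practical downside is tracing participants already transferred to the local TB programme.

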6.3 Instructions for Evaluations

All clinical and laboratory information required by this protocol is to be present in the source documents. Sites must refer to the Source Document Guidelines on the DAIDS Web site for information about what must be included in the source document: <https://www.niaid.nih.gov/sites/default/files/sourcedocappndx.pdf>.

All stated evaluations are to be recorded on the CRF and keyed into the database unless otherwise specified. This includes events that meet the International Conference on Harmonisation (ICH) definitions for a serious AE:

- Results in death
- Life-threatening
- Requires inpatient hospitalization or prolongation of existing hospitalization
- Results in persistent or significant disability/incapacity
- Congenital anomaly/birth defect
- Other important medical event (may not be immediately life-threatening or result in death or hospitalization but may jeopardize the participant or may require intervention to prevent one of the events listed above).

To grade diagnoses, signs and symptoms, and laboratory results, sites must refer to the DAIDS Table for Grading the Severity of Adult and Pediatric Adverse Events (DAIDS AE Grading Table), Version 1.0, December 2004 (Clarification, August 2009), which can be found on the DAIDS RSC Web site: <http://rsc.tech-res.com/clinical-research-sites/safety-reporting/daids-grading-tables>.

Step 1

6.3.1 Sputum Samples

Spot Sputum Collection

Spot sputum will be collected for the following:

AFB Microscopy

Direct microscopy for acid-fast bacilli will be performed and reported as negative, or as scanty, 1+, 2+, or 3+ positive, according to IUATLD scale.

Genotypic DST with HAIN MTBDRplus

Hain MTBDRplus testing for detection of INH resistance (*inhA* or *katG* mutations) and RIF resistance (*rpoB* mutations) will be performed.

Culture and Phenotypic DST Determination with MIC

Phenotypic DST for INH and RIF using the proportion method. The MIC for INH will be determined.

6.3.2 Hospitalization

At the discretion of the investigator, a participant may be hospitalized during the screening period if necessary for the safety of the participant or to decrease risk of transmission to others.

Step 2

6.3.3 Documentation of HIV Status

Section 4.3.5 provides assay requirements for HIV-1 status documentation. HIV status will not be reported on a CRF.

6.3.4 Medical History

The medical history must include all diagnoses identified by the ACTG criteria for clinical events and other diagnoses. For current criteria, refer to the appendix identified in the study CRF. Allergies to any medications and their formulations must be documented.

6.3.5 Medication History

A medication history must be present, including start and stop dates. The table below lists the medications that must be included in the history.

Table 6.3.5-1: Medication History

Category	Timeframe	Location
TB treatment	Complete history, including doses	TB Medication History CRF
ART	Within 30 days prior to entry, including doses	Antiretroviral Medication History CRF
Prescription drugs for treatment of opportunistic infections	Within 30 days prior to entry	CRF
Prescription drugs for prophylaxis of opportunistic infections	Within 30 days prior to entry	CRF
Prescription drugs (other)	Within 30 days prior to entry	CRF

Category	Timeframe	Location
Alternative therapies	Within 30 days prior to entry	Record as yes/no on CRF; if yes, record details in source document
Dietary supplements	Within 30 days prior to entry	CRF

6.3.6 Clinical Assessments

Complete Physical Examination

A complete physical examination will include at a minimum an examination of the skin, head, mouth, neck and lymph nodes; auscultation of the chest; cardiac exam; abdominal exam; examination of the lower extremities for edema. The complete physical exam will also include signs and symptoms, diagnoses, and vital signs (temperature, pulse, respiration rate, and blood pressure). Neurologic examination to evaluate for peripheral neuropathy will be performed.

Targeted Physical Examination

A targeted physical examination will include vital signs (temperature, pulse, respiration rate, and blood pressure). The targeted physical examination is to be driven by any previously identified or new signs or symptoms, including diagnoses that the participant has experienced since the last visit. Neurologic examination to evaluate for peripheral neuropathy will be performed at the final study visit or, for those who discontinue the study early, at the discontinuation visit.

Karnofsky Score

This will be recorded at screening.

Height

Height will be recorded at screening only.

Weight

Weight will be recorded at all visits, except pre-entry.

Signs and Symptoms

At entry, all grades that occurred within 7 days prior to entry must be recorded; post-entry, only signs and symptoms Grade ≥ 2 must be recorded. In addition, all signs and symptoms that lead to a change in treatment must be recorded, regardless of grade.

Diagnoses

Record all diagnoses identified by the ACTG criteria for clinical events and other diseases.

Concomitant Medications

All concomitant medications (as per [section 5.4](#)) started or stopped since the last visit must be recorded on the CRF. Alternative therapies will be recorded as a yes/no on the CRF. If yes, the details will be recorded in the source documents only.

TB Medications

On-study TB treatment: INH will be administered on Days 1-7. At each visit, record all modifications, including start/stop dates, initial doses, and participant-initiated and/or health care provider-mandated modifications, and any permanent discontinuation of study TB treatment.

Standard local TB treatment: Standard local TB treatment will start on Day 8 and no later than Day 10. Record all modifications, including start/stop dates, initial doses, participant-initiated and/or health care provider-mandated modifications, and any permanent discontinuation of TB medications.

Antiretroviral Medications

Record all modifications, including start/stop dates, initial doses, participant-initiated and/or health care provider-mandated modifications, and any temporary holds or permanent discontinuations.

6.3.7 Laboratory Evaluations

Complete Blood Count with Differential

Record all values regardless of grade for: hemoglobin, platelet count, white blood cell count, absolute neutrophil count.

Complete Blood Chemistry Profile

Record all values regardless of grade for: AST, ALT, alkaline phosphatase, total bilirubin, creatinine, potassium, and albumin.

CD4+ Count (HIV-infected participants)

For participants who are HIV-infected, a CD4+ count determination performed within 7 days prior to entry at a DAIDS-approved laboratory must be recorded.

Pregnancy Test

For women with reproductive potential: Serum or urine β -HCG. (Urine test must have a sensitivity of 15-25 mIU/mL.)

NAT2 Genotype

Both whole blood and saliva will be collected for this testing. The sample of saliva will be collected using an Oragene kit.

6.3.8 Chest X-ray

A chest x-ray will be performed at screening, unless the results of a chest x-ray performed within 14 days prior to screening are available.

6.3.9 Sputum Samples

Spot Sputum Collection

Spot sputum will be collected for the following:

Genotypic DST (MTBDRs)

Among those participants with MDR-TB, Hain MTBDRs/ testing for detection of fluoroquinolone **and injectable TB drug resistance** will be performed.

Overnight Sputum Collection

Sputum will be collected over 16 hours each night beginning at around 4pm ±1 hour, and each participant's overnight sputum samples will be pooled in an appropriate, clean container. This sputum will be used for the following:

EBA Analysis by Solid Culture CFU Determination and Liquid MGIT Culture for TTD

Sputum will be cultured on solid media, and CFU count will be determined **for Groups 1 and 2 only. For all groups** daily TTD determination will be done, and measured in hours.

Start and stop times, total volume collected, and any interruptions in collection or temperature control problems will be recorded.

6.3.10 Pharmacokinetic Sampling

See [section 10.0](#), Pharmacology Plan. Blood samples for study drug concentrations may be collected from an indwelling catheter, or if a catheter cannot be placed or maintained successfully, by direct venipuncture.

6.3.11 Hospitalization

At the discretion of the investigator, a participant may be hospitalized during the screening period if necessary for the safety of the participant or to decrease risk of transmission to others.

All participants will be hospitalized for pre-entry and entry visits. Those participants who are randomized to receive treatment will be hospitalized during Days 1-7 to receive treatment and will be discharged from the hospital on Day 8.

